#### 7.5.1.10. PROMIS Sleep Questionnaires

The PROMIS Short Form – Sleep-Related Impairment(8a)/Sleep Disturbance (8b) are both 8-item questionnaires. Each item is rated on a 5-point scale (never, almost never, sometimes, almost always, and always) with a range in score from 8 to 40, with higher scores indicating greater severity of sleep-related impairment/disturbance. Both questionnaires are collected at each study visit starting at Day 1 and through the VC and VCE periods. The recall period will be 7 days. The raw scores on the 8 items should be summed to obtain a total raw score. If more than 4 of the items on the measure are missing, the total score should be set to missing.

After confirming that enough responses were provided, the raw score will be calculated by the below formula:

$$\frac{(Raw\ sum \times number\ of\ items\ on\ the\ short\ form)}{Number\ of\ items\ that\ were\ actually\ answered}$$

If the result is a fraction, then the result will be rounded up to the nearest whole number. The total score will be summarized by treatment and visit.

#### 7.5.1.11. Hospital Anxiety and Depression Scale

The HADS is a 14-item questionnaire that assesses the levels of anxiety and depression a person is currently experiencing. There are 7 questions each for measuring anxiety and for measuring depression, with 4 possible responses to each question (responses are scored as 0, 1, 2, or 3).

Separate scores are calculated for anxiety and depression. The recall period will be the past 7 days for both the VC and VCE periods.

The score for the anxiety and depression subscale will be calculated separately as follows: anxiety score = sum of items 1\*, 3\*, 5\*, 7, 9, 11\*, 13\*; and depression score = sum of items 2, 4, 6\*, 8\*, 10\*, 12, 14 where starred items are reverse scored. Missing values will not be imputed. The change from baseline in anxiety and depression score will be summarized by treatment and visit.

### **7.5.2. Secondary Efficacy Analysis**

All secondary efficacy analyses will be conducted in the VC and VCE DB periods, with the exception that proportion of participants achieving IGA-TS and EASI75 which will also be summarized by visit in the escape arm for participants that entered escape arm at Week 8.

#### **7.5.2.1. Continuous Efficacy Endpoints**

By-visit or by-timepoint summary statistics for the following continuous measurements, including change from baseline and percentage change from baseline, will be presented:

- EASI score
- Itch NRS score
- Current itch score on Day 1
- Skin Pain NRS score
- PROMIS Short Form – Sleep-Related Impairment 8a score
- PROMIS Short Form – Sleep Disturbance 8a score
- AD-affected %BSA
- Total POEM score
- Total DLQI score
- EQ-5D-5L score
- SCORAD score
- HADS score
- WPAI-AD score

Summary statistics including sample size, mean, median, standard deviation, minimum, maximum, first quartile, and third quartile will be presented by visit or timepoint. An MMRM may be fit for the comparisons between ruxolitinib 1.5% cream BID and the vehicle cream group at Week 8. The MMRM will include the fixed effect of baseline, treatment, stratification factors, the visit, and treatment-by-visit interaction. The variance-covariance matrix of the within-participant errors in MMRM will be modeled as unstructured.

For the above continuous measurements during the VCE DB period, only summary statistics will be presented.

### 7.5.2.2. Categorical Efficacy Endpoints

For the following categorical parameters, summary statistics including sample size, frequency, and percentages will be presented by visit or timepoint:

- Proportion of participants achieving EASI75
- Proportion of participants achieving an IGA-TS
- Proportion of participants with a  $\geq 4$ -point improvement in Itch NRS score
- Proportion of participants achieving with a  $\geq 2$ -point improvement in current Itch NRS score at 5, 15, 30, 45, and 60 minutes and 2, 4, and 6 hours post-initial dose on Day 1
- Proportion of participants achieving with a  $\geq 4$ -point improvement in current Itch NRS score at 5, 15, 30, 45, and 60 minutes and 2, 4, and 6 hours post-initial dose on Day 1
- Proportion of participants achieving EASI50
- Proportion of participants achieving EASI90
- Proportion of participants achieving both EASI75 and IGA-TS
- Proportion of participants concurrently meeting all of the following criteria:  
IGA score  $\geq 3$ , EASI score  $\geq 16$ , Itch NRS score  $\geq 4$ , BSA  $\geq 10\%$ , and DLQI score  $> 10$
- Proportion of participants who achieve  $\geq 4$ -point improvement in DLQI from baseline

A CMH test stratified by stratification factors may be performed at Week 8. Stratum-adjusted rate differences (ruxolitinib 1.5% cream BID vs vehicle cream BID) may be provided. The NRI may be used to impute postbaseline missing values in VC period for binary outcomes based on IGA, Itch NRS, and EASI scores.

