6.5.2. Criteria for Permanent Discontinuation of Study Cream

Participants must permanently discontinue study cream if they meet any of the following criteria:

- Occurrence of an AE that is related to treatment with the study cream that, in the judgment of the investigator or the medical monitor, compromises the participant's ability to continue study-specific procedures or is considered to not be in the participant's best interest
- Worsening of AD that requires treatment with a prohibited concomitant medication
- Any Grade 4 laboratory abnormality (see [Table 7](#)) considered related to the study cream
- Persistent AE requiring an interruption of study cream for more than 2 weeks without resolution of the AE

See Section [7](#) for discontinuation procedures.

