**Table 1: Objectives and Endpoints (Continued)**

Objectives	Endpoints
Secondary (continued)	
To further evaluate the efficacy of ruxolitinib cream in participants with moderate AD who had an inadequate response to, or are intolerant to, or contraindicated to TCSs and TCIs (continued).	
 
• Change from baseline (pre-study cream application) in current Itch NRS score at 5, 15, 30, 45, and 60 minutes and 2, 4, and 6 hours post-initial dose on Day 1.
 
• The binary response status of achieving at least a 2-point decrease from baseline in current Itch NRS score at 5, 15, 30, 45, and 60 minutes and 2, 4, and 6 hours post-initial dose on Day 1.
 
• The binary response status of achieving at least a 4 point decrease from baseline in current Itch NRS score at 5, 15, 30, 45, and 60 minutes and 2, 4, and 6 hours post-initial dose on Day 1.
 
• The binary response status of EASI50 from baseline at each postbaseline visit. (EASI50 is defined as achieving <math>\geq 50\%</math> improvement in EASI score.)
 
• The binary response status of EASI90 from baseline at each postbaseline visit. (EASI90 is defined as achieving <math>\geq 90\%</math> improvement in EASI score.)
 
• The binary response status of both EASI75 from baseline and IGA-TS at each postbaseline visit.
 
• Change from baseline at each postbaseline visit for the following: 
 
– AD-affected %BSA
 
– EASI score
 
– SCORAD score
 
– Itch NRS score
 
– Skin Pain NRS score
 
 
 
• Time to open-label escape arm (defined as not achieving 50% improvement in EASI score from baseline at 2 consecutive visits at least 1 week apart)
 
• The binary response status of participants concurrently meeting all of the following criteria at each postbaseline visit: IGA score <math>\geq 3</math>, EASI score <math>\geq 16</math>, Itch NRS score <math>\geq 4</math>, BSA <math>\geq 10\%</math>, and DLQI score <math>> 10</math>.
 
• Time to concurrently meeting all of the following criteria: IGA score <math>\geq 3</math>, EASI score <math>\geq 16</math>, Itch NRS score <math>\geq 4</math>, BSA <math>\geq 10\%</math>, and DLQI score <math>> 10</math>.
 
• The binary response status of experience a relapse after study treatment discontinuation. (The binary response status of participants among EASI75 responders who are on study treatment at Week 24 who meet relapse criteria [loss of EASI50 from baseline] at the safety follow-up visit)
 

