#### **4.1.5. Handling of Missing and Incomplete Data**

In general, values for missing dates will not be handled unless methods for handling missing dates are specified in this section or relevant sections. The original reported dates collected on the eCRF should be used in all relevant listings. The following rules will be used for handling partial dates for analyses requiring dates.

For response endpoints, all nonresponders, as well as all participants who are missing postbaseline values at Week 8, will be defined as nonresponders for the NRI analysis.

For continuous endpoints, any participant who is missing postbaseline values may have missing data handled using MMRM or MI under the missing-at-random assumption. The MMRM model implicitly adjusts for missing data through a variance-covariance structure.

For other endpoints, missing observations will be handled as detailed in the specific sections addressing each analysis.

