**Table 4: Primary Estimand**

Estimand Attribute	Definition		
Treatment effect	Ruxolitinib 1.5% cream BID vs vehicle cream BID		
Population	Participants with moderate AD who had an inadequate response to, or are intolerant to, or contraindicated to TCSs and TCIs (as defined by study inclusion/exclusion criteria)		
Variable	Apply to the coprimary endpoints		
Intercurrent events	Events	Strategy	Rationale (if needed)
	Treatment discontinuation due to any reason	Composite strategy	Participants who discontinue treatment due to any reason prior to Week 8 will be considered as treatment failures (ie, nonresponders) after the intercurrent event. Therefore, composite strategy is used for this type of intercurrent event.
Population-level summary	Stratum-adjusted response proportions difference between–treatment groups		

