Table No.	Title	Population	Standard
2.2.17.2	Summary of Participants concurrently having IGA Score $\geq 3$ , EASI Score $\geq 16$ , Itch NRS Score $\geq 4$ , BSA $\geq 10\%$ , and DLQI Score $> 10$ in the DB Treatment Period	ITT	
2.2.18	Summary of Participants Achieving EASI75 in the Escape Arm	VCE Escape (Entered escape arm at Week 8)	
Itch NRS Score			
2.3.1	Summary and Analysis of Participants Achieving $\geq 4$ -Point Improvement in Itch NRS Score in the VC Period	ITT	
2.3.2	Summary and Analysis of Participants with ITCH4 From Baseline to Day 7 in the VC Period	ITT	
2.3.3	Summary and Analysis of Participants With ITCH4 From Baseline to Day 3 in the VC Period	ITT	
2.3.4	Summary and Analysis of Participants With ITCH4 From Baseline to Day 2 in the VC Period	ITT	
2.3.5.1	Summary and Analysis of By-Visit Itch NRS Score in the VC Period	ITT	
2.3.5.2	Summary of By-Visit Itch NRS Score in the VCE DB Treatment Period	VCE Primary	
2.3.6	Summary and Analysis of Time to $\geq 2$ -Point Improvement in Itch NRS Score in the VC Period	ITT	
2.3.7	Summary and Analysis of Time to $\geq 4$ -Point Improvement in Itch NRS Score in the VC Period	ITT	
2.3.8	Summary and Analysis of Daily Itch NRS Score in the VC Period	ITT	X
SCORAD			
2.4.1.1	Summary and Analysis of By-Visit SCORAD Total Score in the DB Treatment Period	ITT	
Current Itch NRS			
2.5.1	Summary and Analysis of By-timepoint Current Itch on Day 1	ITT	
2.5.2	Summary and Analysis of Participants Achieving $\geq 2$ -Point Improvement in Current Itch NRS Score on Day 1	ITT	
2.5.3	Summary and Analysis of Participants Achieving $\geq 4$ -Point Improvement in Current Itch NRS Score on Day 1	ITT	
Skin Pain NRS Score			
2.6.1.1	Summary and Analysis of By-Visit Skin Pain NRS Score in the VC Period	ITT	
2.6.1.2	Summary and Analysis of By-Visit Pain NRS Score in the VCE DB Treatment Period	VCE Primary	
2.6.2	Summary and Analysis of Daily Skin Pain NRS Score in the VC Period	ITT	X
DLQI			
2.7.1	Summary and Analysis of By-Visit Total DLQI Score in the DB Treatment Period	ITT	
2.7.3	Summary and Analysis of Participants Achieving $\geq 4$ -Point Improvement in DLQI From Baseline in the DB Treatment Period	ITT	
Patient-Oriented Eczema Measure			
2.8.1	Summary and Analysis of By-Visit Total POEM Score in the DB Treatment Period	ITT	
2.8.3	Summary of Participants in Each Category of POEM Score in the DB Treatment Period	ITT	
EQ-5D-5L			

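### SAP 7.5.2.2 permits nonresponder imputation without excepting the five-criteria severity endpoint, where a literal reading scores missing participants as not severe and can bias the comparison in either direction

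*SAP*

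**What the plan says.** SAP Table 1 includes among the secondary endpoints "The binary response status of participants concurrently meeting all of the following criteria at each postbaseline visit", the criteria being IGA ≥3, EASI ≥16, Itch NRS ≥4, BSA ≥10% and DLQI >10. SAP 7.5.2.2 repeats it as "Proportion of participants concurrently meeting all of the following criteria", in a list whose other nine entries are all improvements (EASI50, EASI75, EASI90, IGA-TS, EASI75 with IGA-TS, three itch responses and a DLQI response).

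On missing data, the same section says: "The NRI may be used to impute postbaseline missing values in VC period for binary outcomes based on IGA, Itch NRS, and EASI scores". It names no exception. SAP 4.1.5 gives the coding: "For response endpoints, all nonresponders, as well as all participants who are missing postbaseline values at Week 8, will be defined as nonresponders". The sentence goes on to limit this to the NRI analysis, so it defines how NRI codes a missing value where NRI is used; it does not impose NRI on every binary endpoint.

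Elsewhere the word has a clinical meaning. In SAP Table 4, participants who stop treatment before Week 8 "will be considered as treatment failures (ie, nonresponders) after the intercurrent event".

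The planned output is Table 2.2.17.2 in SAP Appendix A, whose title begins "Summary of Participants concurrently having IGA Score". For testing, 7.5.2.2 says: "A CMH test stratified by stratification factors may be performed at Week 8".

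**The concern.** For nine of the ten endpoints, coding a missing value as nonresponse counts it against the participant's treatment, which is why NRI is regarded as conservative. For the five-criteria endpoint, the response in Table 1 is having the severe state. Nonresponse then means not having it, so the same rule records a missing participant as a good outcome.

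The participants affected include some whom the endpoint is meant to capture. Protocol 7.1.1 requires treatment to stop when the AD to be treated exceeds 20% BSA, and Protocol 6.5.2 lists as a reason for permanent discontinuation: "Worsening of AD that requires treatment with a prohibited concomitant medication". Such a participant with no Week 8 data would be recorded as free of the severe state.

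The entry criteria sharpen this. Protocol 5.1 requires IGA 3, BSA 10% to 20%, Itch NRS ≥4 and DLQI >10. Every participant in the baseline EASI ≥16 stratum therefore meets all five criteria at entry. Literal NRI would move a dropout from that stratum from met to not met with no observed improvement.

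The endpoint also bears on the study rationale. Protocol 2.2 says that the cream may spare or delay systemic therapy, and Protocol 4.1 uses four of the five criteria as the point at which investigators should consider alternatives such as systemic therapy.

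**Working it through.** **The plan's own figures.** The documents state no rate, effect or power for this endpoint. The power claims in SAP Table 2 concern six other endpoints; they reproduce (Fisher exact, 150 vs 75, two-sided 0.05: lowest 97.8%, for ITCH4 on Day 2, against the stated >95%) and do not bear on this point.

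**Formulas.** For each arm (V vehicle, R ruxolitinib), let d be the share missing, s the share of observed participants meeting the criteria, and q the share of missing participants who would have met them. A positive vehicle-minus-ruxolitinib difference is a benefit.

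- True: [(1−dV)sV + dV·qV] − [(1−dR)sR + dR·qR]
- Literal NRI (missing = not met): (1−dV)sV − (1−dR)sR
- Bias of literal NRI: −(dV·qV − dR·qR)
- Missing = met: (1−dV)sV + dV − (1−dR)sR − dR
- Observed cases: sV − sR

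The observed rates s cancel out of the NRI bias. Its sign depends only on which arm loses the larger share of its randomized participants while severe.

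**Worked case.** All rates are assumptions: d = 15% vehicle and 5% ruxolitinib, s = 20% and 5%, q = 60% in both arms.

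- Literal NRI: 0.20 × 0.85 = 17.0%; 0.05 × 0.95 = 4.75%; difference 12.25 points
- True: 17.0 + 0.60 × 15 = 26.0%; 4.75 + 0.60 × 5 = 7.75%; difference 18.25 points
- Bias: −(0.15 × 0.60 − 0.05 × 0.60) = −6.0 points

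With q = 30%, the true rates are 21.5% and 6.25%, a difference of 15.25 points.

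| Method | Vehicle | Ruxolitinib | Difference | Error if q = 60% (true 18.25) | Error if q = 30% (true 15.25) |
|---|---|---|---|---|---|
| Literal NRI | 17.0% | 4.75% | 12.25 | −6.0 | −3.0 |
| Observed cases | 20.0% | 5.0% | 15.0 | −3.25 | −0.25 |
| Missing = met | 32.0% | 9.75% | 22.25 | +4.0 | +7.0 |

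**Range with more missing on vehicle.** With a common q, the understatement is q × (dV − dR). For dV of 10% to 20%, dR of 5% to 8% and q of 30% to 60%, fully crossed:

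- smallest: 0.30 × (10 − 8) = 0.6 points
- largest: 0.60 × (20 − 5) = 9.0 points

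**Other dropout patterns.** Assumed s = 25% vehicle and 5% ruxolitinib; differences in points.

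| d, ruxolitinib / vehicle | q | True | Literal NRI | NRI bias | Missing = met | Observed cases |
|---|---|---|---|---|---|---|
| 5% / 20% | 60% | 24.25 | 15.25 | −9.0 | 30.25 | 20.0 |
| 5% / 15% | 50% | 21.5 | 16.5 | −5.0 | 26.5 | 20.0 |
| 10% / 10% | same as s in each arm | 20.0 | 18.0 | −2.0 | 18.0 | 20.0 |
| 10% / 10% | 50% | 18.0 | 18.0 | 0 | 18.0 | 20.0 |
| 15% / 5% | 50% | 14.5 | 19.5 | +5.0 | 9.5 | 20.0 |

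For the last row: 0.95 × 25 − 0.85 × 5 = 19.5 under literal NRI; adding 0.50 × 5 − 0.50 × 15 = −5.0 gives 14.5. None of the three simple methods is unbiased throughout. Observed cases come closest in the first three rows but not in the last two.

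**The case against.** The strongest reply is that the SAP does not commit to the adverse coding. NRI only may be used; its stated scope names IGA, Itch NRS and EASI but not BSA or DLQI, two of the five components; and 4.1.5 applies only where an NRI analysis is done. The primary estimand equates nonresponder with treatment failure, and a programmer who carried that meaning over would code a dropout as meeting the criteria. This stands in part. It shows that reversed coding is one permitted reading and not a settled instruction. It does not remove the problem, because two programmers could follow the same text and produce opposite data, and the literal reading is the unsuitable one.

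The stakes are also limited. Table 2.2.17.2 is titled as a summary, whereas the EASI and IGA-TS responder tables are titled as summary and analysis. The Week 8 test is optional, and the endpoint lies outside the fixed testing sequence. Worsening can also be picked up elsewhere: the ET1 visit collects IGA, EASI, BSA and DLQI, and NRI is not specified for the companion endpoint in SAP 7.5.2.3 (time to meeting the same criteria). All of this stands and limits the weight of the point.

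A reader might infer that the SAP necessarily understates the benefit over vehicle. The documents do not support that. They give no dropout or severity rates by arm. Understatement is plausible, given the response rates assumed in SAP Table 2, but it requires that more vehicle participants leave while severe.

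**Conclusion.** The point holds as a defect of specification with a conditional bias. The SAP permits NRI for a group of outcomes that can include an unfavourable endpoint, makes no exception for it, and on a literal reading scores missing participants as not severe.

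The size rests wholly on assumed rates: an understatement of 0.6 to 9.0 points if vehicle has more missing data and the severe share among the missing is the same in both arms, no bias if the two arms lose equal shares while severe, and an overstatement (5.0 points in the example) if ruxolitinib loses more.

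It would also be wrong to infer that reversing the code cures the problem. Missing = met overstates the difference by 4.0 points in the worked case and by 7.0 when q is 30%.

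The coprimary and key secondary conclusions are unaffected. The change is still worth making because it is cheap and removes a coding with no clinical rationale for this endpoint.

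**What to change.** State in SAP 7.5.2.2 and 4.1.5 that NRI, in the sense of missing = criteria not met, does not apply to the five-criteria endpoint (Table 2.2.17.2). Make observed-case rates the main summary, with the number missing by arm at each visit. Show two sensitivity analyses beside it: treatment discontinuation counted as criteria met, and multiple imputation of the component scores with the endpoint derived afterwards. Neither should replace the main summary, since missing = met is itself biased. Settle this before the primary database lock, after which the sponsor is unblinded.

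The cost is a sentence in each of two sections, one derivation flag and a few extra outputs. SAP Appendix B already has imputation code for IGA and EASI; by-visit itch, BSA and DLQI would need models. The downside is that observed-case rates assume that dropouts resemble completers, which is why the numbers missing and the sensitivity analyses belong beside them.

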### 7.5.2.3. Time-to-Event Efficacy Endpoints

The following time-to-event endpoints will be analyzed:

- Time to achieve ITCH4 during the VC period.
- Time to achieve ITCH2 during the VC period.
- Time to open-label escape arm  
(defined as not achieving 50% improvement in EASI score from baseline at 2 consecutive visits at least 1 week apart, with the earliest possible time to enter escape arm being at the Week 8 visit)
- Time to concurrently meeting all of the following criteria: IGA score  $\geq 3$ , EASI score  $\geq 16$ , Itch NRS score  $\geq 4$ , BSA  $\geq 10\%$ , and DLQI score  $> 10$ .

For the time to open-label escape arm analysis, the start time will be set to the Week 8 date and only the participants who entered VCE period will be considered as at risk. Participants who were incorrectly assigned to escape arm without meeting the criteria will be censored at the date of their first dose in the escape arm.

A log-rank test stratified by randomization stratification factors will be used for between treatment group comparisons. The hazard ratio and its 95% CI will be estimated based on the stratified Cox regression model using Efron's method accounting for ties. Kaplan-Meier curves will be presented by treatment group. The number of participants, number of events, and number of censoring will be summarized by treatment group. The Kaplan-Meier estimate of median time will be presented with its 95% CI. The 95% CI will be calculated using the method by Brookmeyer and Crowley (1982).

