
To further evaluate the efficacy of ruxolitinib cream in participants with moderate AD who had an inadequate response to, or are intolerant to, or contraindicated to TCSs and TCIs (continued).
	
 • Proportion of participants achieving at least a 4-point decrease from baseline in current Itch NRS score at 5, 15, 30, 45, and 60 minutes and 2, 4, and 6 hours post-initial dose on Day 1. • Proportion of participants with EASI50 from baseline at each postbaseline visit. (EASI50 is defined as achieving $\geq 50\%$ improvement in EASI score.) • Proportion of participants with EASI90 from baseline at each postbaseline visit. (EASI90 is defined as achieving $\geq 90\%$ improvement in EASI score.) • Proportion of participants achieving both EASI75 from baseline and IGA-TS at each postbaseline visit. • Change from baseline at each postbaseline visit for the following: 
 – AD-affected %BSA – EASI score – SCORAD score – Itch NRS score – Skin Pain NRS score • Time to open-label escape arm (defined as not achieving 50% improvement in EASI score from baseline at 2 consecutive visits at least 1 week apart) • Proportion of participants concurrently meeting all of the following criteria at each postbaseline visit: IGA score ≥ 3, EASI score ≥ 16, Itch NRS score ≥ 4, BSA $\geq 10\%$, and DLQI score > 10. • Time to concurrently meeting all of the following criteria: IGA score ≥ 3, EASI score ≥ 16, Itch NRS score ≥ 4, BSA $\geq 10\%$, and DLQI score > 10. • Proportion of participants who experience a relapse after study treatment discontinuation. (proportion of participants among EASI75 responders who are on study treatment at Week 24 who meet relapse criteria [loss of EASI50 from baseline] at the safety follow-up visit) • Time to first re-treatment during the VCE period. • Proportion of time off study treatment due to lesion clearance during the VCE period by visit. • Proportion of time on study treatment during the VCE period by visit.

Table 5: Objectives and Endpoints (Continued)

Objectives	Endpoints

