5.1. Inclusion Criteria

Participants are eligible to be included in the study only if all of the following criteria apply:

1. Adults aged ≥ 18 years at screening (Note: Legal adult age for Korea is ≥ 19 years).
2. Diagnosis of AD as defined by the Hanifin and Rajka (1980) criteria.
3. AD duration of at least 2 years.
4. IGA score of 3 at screening and Day 1.
5. EASI score > 7 at screening and Day 1.
6. Itch NRS score ≥ 4 at Day 1, defined as the average of the 7 days directly before Day 1, with Itch NRS values available for at least 4 of the 7 days.
7. %BSA (excluding the scalp) with AD involvement of at least 10% and up to 20% at screening and Day 1.
8. DLQI score > 10 at screening and Day 1.
9. Documented recent history (within 12 months before the screening visit) of inadequate response, intolerance, or contraindication to TCSs and TCIs (see Section 6.6.1) as follows:
 - a. Inadequate response:
 - For TCSs: Inability of a given TCS to induce and maintain remission or to contain the AD severity at an acceptable level (comparable to IGA score of 0 [clear] or 1 [almost clear]) despite treatment for 28 days or for the maximum duration recommended by the product prescribing information (eg, 14 days for superpotent TCSs), whichever is shorter
and
 - For TCIs: Inability of a given TCI to induce and maintain remission or to contain the AD severity at an acceptable level (comparable to IGA score of 0 [clear] or 1 [almost clear]) despite treatment according to the product prescribing information.

Note: Documented (within 12 months before the screening visit) systemic treatment for AD (eg, oral corticosteroids, cyclosporine, methotrexate, azathioprine, mycophenolate mofetil) or phototherapy or photo(chemo)therapy can also be considered as a surrogate for inadequate response to TCSs and TCIs.

- b. Intolerance: Clinically relevant side effects, safety risks, or skin tolerability issues that outweigh the potential treatment benefits and are the reason why a topical treatment could not be restarted or continued.

Note: Documented history (more than 12 months prior to the screening visit) of clinically significant adverse reactions with use of TCSs and/or TCIs that in the opinion of the investigator outweigh the benefits of restarting treatment would also be considered as evidence of intolerance.

- c. Contraindication: As defined in the product prescribing information.

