2.1.8	Summary and Analysis of Participants Achieving IGA-TS by Region (ROW or Europe) in the DB Treatment Period	ITT	
2.1.9	Summary and Analysis of Participants Achieving IGA-TS by Prior Systemic or Phototherapy in the DB Treatment Period	ITT	
2.1.10	Summary and Analysis of Participants Achieving IGA-TS by Season Enrolled in the DB Treatment Period	ITT	
2.1.11.1	Summary and Analysis of Participants Achieving an IGA Score of 0 or 1 in the DB Treatment Period	ITT	
2.1.12.1	Summary of Participants in Each Category of IGA Score in the DB Treatment Period	ITT	
2.1.13.1	Summary of Participants Achieving IGA-TS in the Escape Arm	VCE Escape (Entered escape arm at Week 8)	
EASI			
2.2.1	Summary and Analysis of Participants Achieving EASI75 in the DB Treatment Period	ITT	
2.2.2	Summary and Sensitivity Analysis of Participant Achieving EASI75 at Week 8 by Multiple Imputations	ITT	
2.2.3	Summary and Analysis of Participants Achieving EASI75 in the VC Period	PP	
2.2.4	Summary and Analysis of Participants Achieving EASI75 by Baseline EASI Score in the DB Treatment Period	ITT	
2.2.5	Summary and Analysis of Participants Achieving EASI75 by Age in the Blinded Treatment Period	ITT	
2.2.6	Summary and Analysis of Participants Achieving EASI75 by Sex in the DB Treatment Period	ITT	
2.2.7	Summary and Analysis of Participants Achieving EASI75 by Race in the DB Treatment Period	ITT	
2.2.8	Summary and Analysis of Participants Achieving EASI75 by Region (ROW or Europe) in the DB Treatment Period	ITT	
2.2.9	Summary and Analysis of Participants Achieving EASI75 by Prior Systemic or Phototherapy in the DB Treatment Period	ITT	
2.2.10	Summary and Analysis of Participants Achieving EASI75 by Season Enrolled in the DB Treatment Period	ITT	
2.2.11	Summary and Analysis of Participants Achieving EASI50 in the DB Treatment Period	ITT	
2.2.12	Summary and Analysis of Participants Achieving EASI90 in the DB Treatment Period	ITT	
2.2.13.1	Summary and Analysis of By-Visit EASI Score in the DB Treatment Period	ITT	
2.2.14.1	Summary of Participants in Each Category of EASI Score in the DB Treatment Period	ITT	
2.2.15	Summary and Analysis of Participants achieving both EASI 75 and IGA-TS in the DB Treatment Period	ITT	
2.2.16	Summary and Analysis of Time to Open-Label Escape Arm	Participants who entered VCE period	
2.2.17.1	Summary and Analysis of Time to concurrently having IGA Score $\geq 3$ , EASI Score $\geq 16$ , Itch NRS Score $\geq 4$ , BSA $\geq 10\%$ , and DLQI Score $> 10$	ITT	

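### Time to meeting all five severity criteria is analysed in ITT with no origin or at-risk rule, although every eligible participant with baseline EASI ≥ 16 already meets all five on Day 1

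*SAP*

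**What the plan says.** The endpoint is listed in SAP Section 7.5.2.3 as "Time to concurrently meeting all of the following criteria", namely IGA ≥ 3, EASI ≥ 16, Itch NRS ≥ 4, BSA ≥ 10% and DLQI > 10. That section applies a log-rank test and Cox model, both stratified by the randomization factors, and Kaplan-Meier curves by treatment group. Appendix A, Table 2.2.17.1 ("Summary and Analysis of Time to concurrently having IGA Score" and the other four criteria) assigns the ITT population.

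For time to the escape arm, the same section fixes the start at Week 8, states that "only the participants who entered VCE period will be considered as at risk", and gives a censoring rule. It has no counterpart for the five-criteria endpoint.

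Protocol Section 5.1 requires, among other things:
- "IGA score of 3 at screening and Day 1"
- Itch NRS ≥ 4, "defined as the average of the 7 days directly before Day 1"
- BSA "with AD involvement of at least 10% and up to 20% at screening and Day 1"
- "DLQI score > 10 at screening and Day 1"

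EASI need only exceed 7. Randomization is stratified at EASI 16.

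The companion binary endpoint in Protocol Section 3 is explicit about timing: "Proportion of participants concurrently meeting all of the following criteria at each postbaseline visit". The time-to-event endpoint carries no such limit.

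**The concern.** A time-to-event analysis needs participants who are free of the event at the origin. Here one randomization stratum is in the event state before the first application, in both arms, and the plan does not say how to treat it.

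The result invites a particular reading. Protocol Section 2.2 suggests that the cream may postpone or avoid systemic treatment, and Protocol Section 4.1 uses four of these five criteria (all but DLQI) as the prompt to consider systemic therapy. A hazard ratio below 1 would naturally be taken as a delay in reaching that point. For participants who were there on Day 1, it would instead reflect how quickly they left.

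**Working it through.** **Step 1. Compare the event with the entry criteria.**

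| Event criterion | Required on Day 1 (Protocol 5.1) | Guaranteed at entry? |
|---|---|---|
| IGA ≥ 3 | IGA = 3 | Yes |
| Itch NRS ≥ 4 | 7-day average ≥ 4 | Yes |
| BSA ≥ 10% | 10% to 20%, scalp excluded | Yes |
| DLQI > 10 | DLQI > 10 | Yes |
| EASI ≥ 16 | EASI > 7 | Only in the ≥ 16 stratum |

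Two details do not change this. The itch criterion uses the same 7-day average as the by-visit baseline in SAP Section 7.4.1.1; a single last daily score could fall below 4, but that is the baseline for daily itch analyses. Excluding the scalp can only make entry BSA smaller than total BSA. So four of five criteria hold for every eligible participant, and five of five for every eligible participant with baseline EASI ≥ 16.

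**Step 2. If Day 1 counts.** Take the ≥ 16 stratum with n1 and n2 participants per arm and N = n1 + n2. All fail at time 0, so d = N.
- Expected events in arm 1: d × n1/N = n1, so observed minus expected = 0.
- Variance: d × (n1/N) × (n2/N) × (N − d)/(N − 1) = 0, because N − d = 0.

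For example, with n1 = 40 and n2 = 20, expected = 60 × 40/60 = 40, the difference is 0 and the variance is 0. The log-rank test then rests on the < 16 stratum alone. Each Kaplan-Meier curve drops at time 0 by the stratum's share, and its median is 0 once that share reaches 50%.

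**Step 3. If any postbaseline visit counts.** All five components are collected at Week 2. A participant in the ≥ 16 stratum who still meets them then is an event, even if an EASI75 and IGA-TS responder at Week 8. Below 16, an event requires EASI to rise to 16 or more. One hazard ratio is estimated across both meanings.

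**Step 4. Illustration. Every rate here is assumed.** There are 75 vehicle and 150 ruxolitinib participants (225 at 2:1), with share s in the ≥ 16 stratum. All five criteria are still met at Week 2 by 50% (vehicle) and 15% (ruxolitinib) of that stratum, with no later events there. New entry below 16 is 5% in both arms, spread evenly over Weeks 2, 4 and 8, so there is no effect on new entry.
- Vehicle events = 75 × [0.50s + 0.05(1 − s)]
- Ruxolitinib events = 150 × [0.15s + 0.05(1 − s)]
- Events from participants positive on Day 1 = 75 × 0.50s + 150 × 0.15s = 60s

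The hazard ratio is from a Cox model stratified by baseline EASI with Efron ties, on a sample enlarged 100-fold.

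| s | In stratum (225s) | Events, vehicle + ruxolitinib | Positive on Day 1 | Hazard ratio |
|---|---|---|---|---|
| 10% | 22.5 | 7.1 + 9.0 = 16.1 | 6.0 (37%) | 0.58 |
| 20% | 45 | 10.5 + 10.5 = 21.0 | 12.0 (57%) | 0.44 |
| 30% | 67.5 | 13.9 + 12.0 = 25.9 | 18.0 (70%) | 0.37 |
| 40% | 90 | 17.3 + 13.5 = 30.8 | 24.0 (78%) | 0.33 |

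With persistence of 30% and 20% instead, the hazard ratio runs from 0.85 (s = 10%) to 0.70 (s = 40%). The result depends heavily on rates that the documents do not give.

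**Step 5. Validity under the null.** With equal persistence (50% in both arms) and equal new entry (5% in both arms), the stratified log-rank test rejects in about 5% of simulated trials at all four shares.

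**The case against.** **The comparison is randomized and stratified by this very factor.** This stands. Step 5 shows the nominal error rate when there is no effect in either stratum. In the Step 4 setting with 50% and 15% persistence, simulated rejection rises from about 17% to about 83% as the share goes from 10% to 40%. A reader might take these as false positives. They are not: the setting contains a real effect in the ≥ 16 stratum, and detecting it is power.

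**Persistence matters clinically, and neither document says that the endpoint measures new entry.** This is fair. Protocol Section 2.2 intends to include participants who would otherwise have been eligible for systemic therapy, and still meeting the criteria on treatment is a relevant failure for them. But the by-visit proportion (Table 2.2.17.2) already shows persistence. Combining it with worsening in one hazard ratio makes neither readable.

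**The context suggests an origin.** SAP Section 4.1.3 treats measurements up to the day of first application as baseline, which favours the postbaseline reading over Step 2. Protocol Section 4.1 raises systemic therapy only at or after Week 8. A Week 8 origin would remove the Week 2 events, but the SAP does not state it. Even then, an event would still mean non-improvement in one stratum and worsening in the other.

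**The endpoint is minor.** This stands. It lies outside the testing sequence in SAP Section 3.2. Protocol Section 10.4.2 specifies log-rank and Cox methods only for ITCH2 and ITCH4.

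**Conclusion.** The point holds as one of definition and interpretation. That the whole eligible ≥ 16 stratum starts in the event state follows from the entry criteria alone, as does the absence of an event-free starting group in ITT. Without an origin, at-risk group and event window, the planned hazard ratio and Kaplan-Meier curve cannot be read as a delay in reaching this state.

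A reader might go further and infer an inflated Type I error, or a known and large distortion. The documents support neither. The comparison is valid when there is no effect in either stratum. The size is unknown, because stratum share, persistence and new-entry rates are all absent; the Step 4 hazard ratios show only what could happen under stated assumptions.

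Severity is minor. Coprimary, key secondary and by-visit results do not change.

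**What to change.** Before the primary database lock, after which the sponsor is unblinded (SAP Section 10), state in SAP Section 7.5.2.3 for this endpoint:

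1. Time runs from Day 1, and only postbaseline visits can be events.
2. The log-rank test, hazard ratio and Kaplan-Meier curve use participants who do not meet all five criteria on Day 1. Stratify by region only, since eligible participants in this group all have baseline EASI < 16.
3. Participants who meet all five on Day 1 are described by the existing by-visit proportion (Table 2.2.17.2), shown by baseline EASI stratum.
4. Systemic therapy, escape-arm entry and discontinuation for worsening are not simply censored. Each is tied to poor disease control, so such censoring is likely to be informative. Treat them as events or competing events, or examine them in a sensitivity analysis.

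The cost is SAP wording, a new population label for Table 2.2.17.1 and one by-stratum display, with no new data. The risk set shrinks to 225 × (1 − s), which is 202.5 at an assumed 10% share and 135 at 40%. At an assumed 5% new entry that gives 202.5 × 0.05 = 10.1 down to 135 × 0.05 = 6.8 events, so the hazard ratio will be imprecise. It also remains sensitive to small EASI changes: a participant at 15.9 who still meets the other four criteria becomes an event at 16.
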